We also know that what you have seen influences what you will report seeing next, for example, in classic adaptation effects (e.g. Helson, 1964) or in serial dependence effects like those studied

by Fischer & Whitney (2014) and many others (e.g. Gekas, McDermott, & Mamassian, 2019 or Manassi, et al., 2021 for work with radiologists). What you are *told* that you will see also has an impact. Thus, you will look harder if you are given information that suggests that it is like that there is something to find (Reed, Chow, Chew, & Brennan, 2014; Littlefair, et al., 2016). In this paper, we examine these effects together. What is the effect of the prevalence in one block on performance on a subsequent block?

Our understanding of prevalence effects was complicated in 2018, when Levari et al. (2018) reported that it was possible to obtain effects in the opposite direction from the classic LPE. Their participants made decisions about a single item on a continuum. For instance, participants might be asked if a dot, drawn from a blue-purple color continuum, was ‘blue’. When fewer dots were drawn from the blue end of the continuum, they reported that participants became more liberal about calling ambiguous dots ‘blue’. They called this effect “Prevalence-induced concept change” (PICC). Lyu et al. (2021) found that one driver of these opposing LPE and PICC results was the presence or absence of feedback. When making decisions about the same stimulus continuum, participants reliably produced LPE effects when given feedback after each trial. They tended to produce PICC effects (somewhat less reliably) when there was no feedback. This has real-world implications because, just as tasks differ in target prevalence, they differ in feedback. For instance, in training, participants might receive immediate feedback after every trial. In the field, that feedback might be delayed, partial, or unavailable. Consider airport security screening. In training, participants are likely to see targets at relatively high prevalence, with feedback. At the airport checkpoint, real ‘threats’ will be rare (we may hope!) and security screens may get some feedback about some positive cases because the suspect bag is opened on the spot. False

negative errors probably generate no feedback, even though these would be the most serious errors in a security setting.

The central question of the present study is how experience with one level of prevalence, with or without feedback, influences performance on subsequent trials where either prevalence and/or feedback conditions could have changed. In the great bulk of research on prevalence effects, high prevalence trials were followed by low prevalence trials or participants experienced only a single prevalence level. Typically, feedback is not independently manipulated (but see Grown & Kukucka, 2021; Lyu, et al., 2021; Papesh, Heisick, & Warner, 2018; Weatherford, Erickson, Thomas, Walker, & Schein, 2020). Moreover, in previous studies, the change due to a previous discrete block of trials was not assessed.

In the present study, prevalence can be high or low and feedback can be present or absent. This yields four conditions: Low prevalence with feedback, Low prevalence without feedback, High prevalence with feedback, and High prevalence without feedback. There are 16 possible pairings of two consecutive blocks. In this study, the stimuli are skin lesions: either nevi (skin 'moles'; singular, nevus) or melanoma (skin cancer). A large dataset of over 300,000 decisions was collected on-line by participants using a medical image labeling app ("DiagnosUs" <http://diagnosus.com/>). Participants had varying levels of expertise from complete novice to MD as will be described later. Thus, in addition to allowing us to assess the influence of one prevalence X feedback combination on another, these data provide new evidence about prevalence effects in expert populations (K K Evans, Birdwell, & [name], 2013; K. K. Evans, Tambouret, Wilbur, Evered, & [name], 2011; Evered, 2017; Mitroff, Ericson, & Sharpe, 2017;

Reed, Ryan, McEntee, Evanoff, & Brennan, 2011; Trueblood, et al., 2021; [name], Brunelli, Rubinstein, & Horowitz 2013).

To anticipate the broad outlines of the results, LPE and weak PICC effects are produced with these dermatology stimuli. As in other studies with expert populations, our experts show these effects, as do novices. In terms of the influence of one block of trials on the next block, we find that, in general, experience with a low prevalence block with feedback makes one more conservative in any subsequent block while the experience of high prevalence with feedback makes one more liberal. A block without feedback does not appear to have a significant impact on the next block.

Methods

Data were collected on-line via a free and open iOS application, “DiagnosUs”, created by Centaur Labs as a platform for game-like image labeling competitions <https://www.centaurlabs.com/>). Between 6/22/21 and 6/27/21, Centaur Labs ran 24 ‘contests’ on our behalf, collecting >300,000 trials from 803 participants in 6 days. Each of the 24 contests consisted of 80 unique images of a skin lesion as shown in Figure 1. This is a relatively small number of images, but it kept the sessions short and encouraged participation. Images came from the International Skin Imaging Collaboration (ISIC) 2018 challenge (Codella, et al., 2019). The set contains over 1,200 melanoma images and over 7,600 nevus images.

[figure not shown]

Figure 1: Sample stimulus displays. Left: Participants are asked if a lesion is a melanoma (cancer) or a nevus (benign ‘mole’). Right: After response, if this were a feedback condition, red or green feedback would inform the observer of the correctness of the answer. In no feedback conditions, neutral feedback indicated that the response had been registered.

On each of the six days, there were four contests available. These were:

- 1) Low Prevalence – No Feedback; consisting of 20% (16) melanoma images
- 2) Low Prevalence – Feedback; prevalence was the same as in #1, but with accurate, trial by trial feedback
- 3) High Prevalence – No Feedback; consisting of 50% (40) melanoma images
- 4) High Prevalence – Feedback; prevalence was the same as in #3, but with accurate, trial by trial feedback

The contests were randomly assigned to participants with the constraint that they did not run the same type of contest more than once in a day. Participants could take part in as many or as few contests as they wished over the course of the six days and they could end up repeating a

condition from one day on another day. The prevalence and feedback conditions were not advertised to participants. Accuracy is the main dependent variable though we also collected response times.

Because of the on-line, voluntary nature of the data collection, we did not have control over the viewing conditions or the type of screen used. We compensated by collecting a very large dataset (see below).

Observers

We collected data from 803 unique individuals. For each individual, we have a crude categorization of expertise as shown in Table 1:

Medical Student	337
Pre-Med Student	174
No Medical Experience	145
Medical Doctor	54
Other Healthcare Professional	47
Nurse	25
Medical Technician	11
Physician Assistant	10

Table 1: Observers divided by expertise category

Participants were asked why they chose to participate and given three choices, as shown in Table 2.

Compete With Others	37
Earn Money	248
Improve My Skills	518

Table 2: Observers divided by reason to participate

Participants reported coming from 78(!) countries with three quarters of the participants coming from nine countries, as shown in Table 3.

Philippines	198
USA	182
Ghana	94
Great Britain	31
Romania	30
Canada	27
Mexico	19
Indonesia	15
Australia	13
All other	194

Table 3: Reported country of origin.

Beyond this demographic information, we have only an observer number. We were given no identifying information about the participants. Participation on the app constituted consent. Procedures were approved by the Institutional Review Board at Brigham and Women's Hospital (IRB #2007P000646).

These 803 participants produced 311,842 trials of data. An excel spreadsheet with all data is posted on the Open Science Framework at <https://osf.io/hck5n/>. From this set, we eliminated participants who did not complete a full block of 80 trials. This left 630 participants who ran a total of 277,371 trials in 2,988 blocks. Different participants chose to participate in different numbers of blocks. As shown in Table 4.

Blocks Run	# of Participants		Blocks Run	# of Participants
1	315		13	10
2	178		14	2
3	104		15	4
4	56		16	6
5	52		17	5
6	22		18	3
7	27		19	10
8	20		20	3
9	14		21	4
10	10		22	2
11	10		23	6
12	5		24	4

Table 4: Numbers of participants who ran N (1-24) blocks over 6 days of testing.

Those participants running only a single block were removed from most analyses because our primary interest is the influence of one block upon the next. Obviously, with some participants contributing 24 blocks and others contributing 2, the dataset is unbalanced. We repeated the main analyses reported below, limiting the analysis to only the first pair of blocks for each observer. This reduces power. However, the main patterns of results, reported below, are found when the dataset is restricted to only blocks 1 and 2. Accordingly, we think that the unequal numbers of trials and blocks from different participants is not a significant issue for the present study. In the results reported, we analyze results from the 2,998 remaining blocks of data.

Statistical Analysis / Results

To analyze the effect of one block on the next block, we derived all the pairs of blocks in the dataset. For each of the blocks, we calculated the true positive and false positive proportions and used these to derive the standard signal detection measure of d' and criterion (Note that we are refraining from using the term “sensitivity” because it is used to refer to d' in the behavioral science community and to the true positive rate in the medical community.) For the primary analyses, pairs were removed from analysis if either member of the pair produced a d' of less than 0.5. The task was relatively difficult and we had little control over the motivation of participants in online study of this sort. The probability of achieving a $d' > 0.5$ by guessing through an 80 trial block is $\sim 0.6\%$. A cutoff of 0.4 would permit over 2% of blocks to be pure guessing. A $d' > 0.5$ cutoff left 2,080 pairs of blocks. The distribution of those pairs is shown in

Table 5:

		Block N				
		Low, No Feedback	Low, Feedback	High, No Feedback	High, Feedback	
Block N+1	Low, No	29	140	151	134	454
	Low, Feed	92	110	150	218	570
	High, No	261	117	51	117	546
	High, Feed	147	218	118	27	510
		529	585	470	496	2080

Table 5: Counts of the 16 different pairs of Block N and Block N+1.

As can be seen, there is a good, if uneven distribution of pairs. There are fewer pairs on the diagonal where the condition is the same in Blocks N and N+1. In order to run the same block, twice in a row, participants needed to encounter that condition last on Day K and first on Day K+1 since the same condition could not be run twice on the same day. The marginals show that this distribution of the four different conditions is very roughly uniform.

First, we compare performance in the four conditions, regardless of their position the sequence of sessions for each observer. Figure 2 shows the signal detection measures of d' and criterion, “c”. These values cannot be computed if $p(\text{True Positive}) = 1.0$ or $p(\text{False Positive}) = 0.0$. Accordingly, in keeping with one standard practice, we add $\frac{1}{2}$ of a False Positive error to each False Positive count (Hautus, Macmillan, & Creelman, 2021).

[figure not shown]

Figure 2: D' and Criterion as a function of condition. Each dot represents one of 2080 blocks of data. Black lines show mean and +/- 95% CI of the mean.

A one-way ANOVA shows a main effect of condition on d' ($F(3, 2076) = 6.461, p = 0.0002$, partial eta-sq = 0.01) and Šídák's multiple comparisons test shows that performance on skin cancer detection task is modestly better in the high prevalence, feedback condition than in the high prevalence, no-feedback condition ($p = 0.008$). Prevalence effects are better understood as criterion shifts. An ANOVA shows a very large main effect of condition on criterion ($F(3, 2076) = 30.16, p < 0.0001$, partial eta-sq = 0.04). Pairwise comparisons show a strong LPE effect when feedback is given ($p < 0.0001$). Criterion becomes more conservative at low prevalence. Without

feedback, criterion becomes slightly more liberal on average (0.34 to 0.31). This is not statistically significant ($p = 0.47$). As noted earlier, the PICC effect (Levari, et al., 2018), while certainly real, is typically more fragile than the LPE effect in the opposite direction (Lyu, et al., 2021). The differences between conditions with feedback and without feedback are highly significant ($p < 0.0001$ for each comparison). A significant LPE effect is seen if analysis is restricted to each participant's first block of data ($p < 0.0001$). There is no PICC effect. If all blocks of data are used, eliminating the $d' > 0.5$ filter, there is, again a significant LPE ($p < 0.0001$) and an insignificant PICC effect ($p = 0.1244$).

Even though participants were not focused on the speed of their responses, response time data reflect the effects of prevalence and feedback. Figure 3A shows the distribution of the ~300,000 trials, divided by block type. As is typical with RT distributions, these distributions have very long positive tails. Some very long RTs probably reflect extended thought, while others might reflect checking an incoming text message. We chose to eliminate the longest 1% of RTs as outliers (>7 sec). Figure 3B shows the mean and 95% confidence intervals on a much finer scale so that the differences between conditions are more clearly visible. There is a significant effect of block type ($F(3, 299422) = 52.88$, $p < 0.0001$, partial eta-sq = 0. 0.0005). Šídák's multiple comparisons test shows that the 46 msec difference between high and low prevalence with feedback is significant ($p < 0.0001$). Low prevalence RTs are shorter than high prevalence. Without feedback, the PICC effect on RT goes in the opposite direction. Low prevalence RTs are 18 msec longer than high prevalence ($p = 0.0008$). These effects are in line with the RT effects seen in other prevalence studies ([name] & VanWert, 2010).

[figure not shown]

Figure 3: Response time as a function of block type. RTs < 7 sec were analyzed. (A) RT distributions with the graph truncated at 3 sec. Black lines show the mean. (B) Mean RT on a much finer scale. Error bars show +95% confidence intervals.

How does one block influence the next?

The block data essentially replicate previous results, collected under very different conditions. However, the key question for this study is whether or not exposure to one combination of prevalence and feedback influences the next block of trials. Blocks could be independent of each other. The effect of one block might have a transient impact on the next block (e.g. lasting for a few trials and then fading). Finally, the effect of one block on the next could be dependent on the delay between blocks (especially since that delay could be from one day to the next.). To assess

each of these effects, we derive measures of d' and criterion for each of the 16 pairs (combinations of one of four 'first blocks' with one of four 'second blocks'). We then subtract a baseline derived from all blocks of the second block condition. We use the second blocks as the baseline because we are looking for a change in the second block. In fact, it doesn't make much difference. Many second blocks in one pair are the first blocks in a subsequent pair and the baselines would be very nearly the same if all blocks were included as in Figure 2 above. Thus, for example, to assess the influence on criterion of Low Prevalence without Feedback (Condition 1 in the figures to follow) on High Prevalence without Feedback (Cond 3), we compute $\text{Criterion}(\text{pair 13}) - \text{Criterion}(\text{Cond 3})$. This is done for each of the 2080 pairs of blocks using the $d' > 0.5$ filter. The data for each of these 2080 "good" pairs of blocks are posted on the Open Science Framework at <https://osf.io/hck5n/>.

Figure 4 shows the change in D' as a function of pair with each dot representing one pair of blocks. Statistical tests are simple T-tests against a null hypothesis of no change in d' from block 1 to block 2. Three pairs, forming no obvious pattern, reach statistical significance (all $p = \sim 0.02$, all Cohen's $d = \sim 0.2$). As these are not corrected for multiple comparisons, these should not be considered strong effects. The general picture is of little or no effect of the first block of trials on d' in the second block of trials.

[figure not shown]

Figure 4: Change in d' on block 2 as a function of the nature of block 1. X-axis gives numerical values for each member of a pair where 1 = low prevalence, no feedback, 2 = low prevalence, with feedback, 3 = high prevalence, no feedback, and 4 = high prevalence, with feedback. P-values show results for simple t-tests, testing against the null hypothesis that there is no change in d' . Black lines show means +/- 95% confidence intervals.

A different pattern is seen in the criterion data, plotted in Figure 5. Here, there are two clear clusters of significant effects. When block 1 has low prevalence and feedback, criterion on block 2 is more conservative (Pairs where Block 1 is low prevalence with feedback, all $p < 0.006$, Cohen's d between 0.2 and 0.5). When block 1 has high prevalence and feedback, criterion on block 2 is more liberal (Pairs where Block 1 is high prevalence with feedback, $p < 0.0005$, pair

44, $p = 0.017$; note that there are only 27 pairs of this variety in the dataset, All Cohen's d between 0.2 and 0.5). When block 1 does not have feedback, there is no effect on criterion in pair 2, except, perhaps, for 'high feedback' on Block 2 ($p < 0.028$, again, not corrected for multiple comparisons, Cohen's $d = 0.18$). This is the main finding of the paper. Criterion can be manipulated by the prevalence of the preceding block of trials, but only if the participants received feedback on that first block.

[figure not shown]

Figure 5: Change in criterion on block 2 as a function of the nature of block 1. P-values
show results for simple t-tests, testing against the null hypothesis that there is no change in
criterion. Black lines show means +/- 95% confidence intervals.

Looking separately at changes in P(True Positive) and P(False Positive) responses, we see essentially the same pattern of results. For changes in True Positive proportions, pairs where Block 1 is low prevalence with feedback are significant (all $p < 0.005$) except when Block 2 is High Feedback ($p = 0.38$). Pairs where Block 1 is high prevalence with feedback are significant (all $p < 0.005$ except when Block 2 is Low Feedback which $p = 0.02$). The Low Feedback – High Feedback pair is not significant. For changes in False Positive proportions, pairs where Block 1 is low prevalence with feedback are significant (all $p < 0.05$). When Block 1 is high prevalence with feedback, results are significant when Block 2 is Low No Feedback, High No Feedback, and Low Feedback ($p < 0.01$). When Block 2 is High Feedback, there is no significant change ($p = 0.29$). The Low No Feedback – High Feedback pair is significant ($p = 0.001$). No other changes in P(True Positive) and P(False Positive) responses are significant. As noted above, removing the $d' > 0.5$ filter does not change the pattern of results. Limiting analysis to only the first pair of blocks for each participant preserves the direction of effects but some effects become statistically unreliable because of the loss of power.

Do the effects of one block on the next change with time between blocks?

Figure 5 shows that a block with feedback has an influence on the criterion in the next block. Is that effect transitory or persistent? The time between blocks is quite variable because participants could perform the second block immediately or from one to several days later. Accordingly, for each of the 16 pairs of blocks, we examined change in criterion as a function of time between blocks. The results are shown for four different time ranges in Figure 6.

[figure not shown]

Figure 6: Change in criterion as a function of time between the start of block 1 and start of block 2. 1440 minutes = 1 day. Colored lines are best-fit linear regressions for each of 16 pairs of block types. A) All data, B) Delay < 1 day, C) Delay < 2 hours, D) Delay < 15 min. Repeat pairs (e.g. Low Feedback -> Low Feedback) do not occur for shorter delays (C & D).

Because the distribution of delays is strongly skewed toward shorter delays, we repeated the regression analysis separately for the whole dataset, for all delays < 1 day (84% of all data), < 2hrs (60% of all data), and 15 min or less (still include 52% of all data because participants tended to do one block and then another, immediately). The four panels of Figure 6 zoom in to smaller and smaller time scales but, in fact, it does not matter. The point of the admittedly noisy Figure 6 is that there is no obvious pattern of slopes. This is borne out by linear regressions for

each of the 16 pairs of block types. For the entire data set (Figure 6A), fourteen of sixteen correlations are not significant (all $r\text{-sq} < 0.02$, all $p > 0.16$). The Low No Feedback -> Low Feedback Pair has a $r\text{-sq}$ of 0.06 ($p = 0.015$). The High Feedback -> Low Feedback Pair has a $r\text{-sq}$ of 0.02 ($p = 0.045$). The regression lines for those conditions are shown as thicker lines in Fig 6A. Examining this relationship, the change in criterion is near zero at short times and the change grows more conservative with time. For delays less than 1 day, no correlations are significant (all $r\text{-sq} < 0.02$, all $p > 0.35$). For delays less than 2 hrs, no correlations are significant (all $r\text{-sq} < 0.02$, all $p > 0.20$). For delays less than or equal to 15 min, no correlations are significant (all $r\text{-sq} < 0.025$, all $p > 0.24$). In sum, there is no evidence for the effects, shown in Figure 4, fading with time. The two (out of 64) significant correlations seem likely to be random fluctuations of the data and go in the 'wrong' direction if the hypothesis under test is that block 1 would influence block 2 if block 2 occurred recently but not after a longer delay.

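### The condition tests on d', criterion and response time leave out variation between image sets, although each condition appears to rest on only six sets

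*Combined protocol and SAP*

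**What the plan says.** The design is in the Specific Protocol, Methods. "Each of the 24 contests consisted of 80 unique images of a skin lesion", and "On each of the six days, there were four contests available", one for each combination of prevalence and feedback. The two prevalence mixes are given as "Low Prevalence – No Feedback; consisting of 20% (16) melanoma images" and "High Prevalence – No Feedback; consisting of 50% (40) melanoma images"; the feedback versions keep the same prevalence. On the image source: "The set contains over 1,200 melanoma images and over 7,600 nevus images".

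The randomisation described is of contests to people: "The contests were randomly assigned to participants", with no repeat of a condition within a day. The section gives no rule for allocating images to contests. It does not say whether the feedback and no-feedback contests of a day shared images, or whether image sets were rotated across conditions.

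Statistical Analysis / Results takes the block as the unit for d' and criterion. The Figure 2 legend reads "Each dot represents one of 2080 blocks of data", and the text continues "A one-way ANOVA shows a main effect of condition on" d', with F(3, 2076) = 6.461. For criterion, F(3, 2076) = 30.16. The RT analysis takes the trial as the unit, with F(3, 299422) = 52.88. No reported analysis includes contest, image set or image.

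**The concern.** Condition is a property of the contest. If everyone in a contest judged the same lesions, each block from that contest carries the same image-set effect. A low-prevalence set has only 16 melanomas, so a few hard or atypical ones would move the hit rate, and with it d' and criterion, for all of that contest's blocks together. The error term for condition should then reflect how much contests differ within a condition. The reported tests use only the scatter of blocks or trials.

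Adding participants averages out differences between people and leaves the number of image sets at six per condition. The size of the dataset is therefore no remedy, and the reported checks (first block only, first pair only, no d' filter) reuse the same contests. What is at stake is whether the d', criterion and RT differences in Figures 2 and 3 extend beyond the particular lesions shown, and whether the intervals in those figures are wide enough.

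**Working it through.** **Inputs from the documents.** Contests: 6 days × 4 = 24, so 24/4 = 6 per condition. Table 5 sums to 2,080 pairs, the number of blocks given for Figure 2. The F values are those above.

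**Reproducing the reported figures.** Error df = 2,080 − 4 = 2,076, which leaves no room for a contest or image term. Partial eta-squared = 3F/(3F + error df).
- d': 19.38/(19.38 + 2,076) = 0.009; p = 0.00024 (reported 0.01 and 0.0002).
- Criterion: 90.48/(90.48 + 2,076) = 0.042; p = 4 × 10⁻¹⁹ (reported 0.04 and < 0.0001).
- RT: 158.64/(158.64 + 299,422) = 0.0005; p < 10⁻³³ (reported 0.0005 and < 0.0001).

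**Feasibility of separate sets.** Twenty-four non-overlapping sets need 12 × 16 + 12 × 40 = 672 melanomas and 12 × 64 + 12 × 40 = 1,248 nevi. Both are within the stated pool.

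**Allowing for image sets.** Treat contest as a random factor nested in condition, with 24 − 4 = 20 error df. Average cluster size is m = 2,080/24 = 86.7 blocks, or 299,426/24 = 12,476 trials for RT. The design effect is DEFF = 1 + (m − 1) × ICC. The adjusted statistic is F/DEFF on F(3,20), with 5% critical value 3.098. The ICC is an assumption, shown as a range:

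| ICC | DEFF (blocks) | Interval width × √DEFF | d' p | Criterion p |
|---|---|---|---|---|
| 0 | 1.00 | 1.0 | 0.003 | 1 × 10⁻⁷ |
| 0.005 | 1.43 | 1.2 | 0.014 | 2 × 10⁻⁶ |
| 0.01 | 1.86 | 1.4 | 0.035 | 0.00001 |
| 0.02 | 2.71 | 1.7 | 0.10 | 0.0002 |
| 0.05 | 5.28 | 2.3 | 0.33 | 0.005 |
| 0.10 | 9.57 | 3.1 | 0.58 | 0.048 |

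The width factors are before replacing 1.96 by the t value on 20 df.

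**Thresholds**, from (F/3.098 − 1)/(m − 1):
- d': (6.461/3.098 − 1)/85.67 = 0.0127.
- Criterion: (30.16/3.098 − 1)/85.67 = 0.102.
- RT: (52.88/3.098 − 1)/12,475 = 0.0013.

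**False-positive rate.** In a simulation with the Table 5 counts, an even spread over days and no true condition effect (1,000 runs per ICC), the block-level ANOVA rejected in 5% of runs at ICC 0, 24% at 0.01, 38% at 0.02, 70% at 0.05 and 85% at 0.10.

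**Carry-over tests.** The same simulation applied the one-sample t-tests after subtracting the pooled mean of second blocks of that condition. Mean rejection was 2.4–2.8% at every ICC, with diagonal pairs at 3.0–5.6%. A second run with a deliberately uneven spread over days gave a mean of 3.8% at ICC 0.05 and 5.4% at 0.10, with diagonal pairs up to 7.1%. Neither run modelled variation among block-1 image sets.

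**The case against.** **The nesting is inferred.** The word unique may mean only that no image repeats within a contest. If each participant had drawn a fresh sample, there would be no shared set to model. If the feedback and no-feedback contests shared images, set differences would not affect the feedback contrast, and 24 sets with 20 df would be the wrong structure. This stands as a condition on the result. One fixed set per contest is still the natural reading, and only the investigators can settle it.

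**Confounding.** A reader might infer that condition effects are confounded with image difficulty. The documents do not support that. They show no non-random allocation, and six sets per condition are replicates from which set variance can be estimated. What they support is an omitted variance component.

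**The main result.** A reader might also infer that the pooled baseline lets image-set difficulty into the carry-over tests (Figures 4 and 5). It largely does not. All four block-1 types that precede a given condition draw their second blocks from the same six contests, so set difficulty mostly cancels, and what remains adds scatter that the t-test already counts. The simulations agree. The reported criterion shifts also keep one direction across all four block-2 conditions in each feedback family, which block-2 difficulty does not readily explain. Still untested is that each block-1 condition also rests on six sets.

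**Weight of the affected results.** The ICC has no anchor in the documents. The authors themselves call the d' difference modest and present the condition comparisons as replication. Wider intervals would not overturn the non-significant no-feedback prevalence contrast on criterion (p = 0.47). All of this limits the reach of the point, but the error term is still incomplete.

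**Conclusion.** The point holds for the condition tests on d', criterion and RT and for the intervals in Figures 2 and 3. They are computed as though the images contributed no shared variation, so any positive between-set variance makes them too narrow.

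The d' effect is fragile: an ICC of about 0.013 (a set-to-set SD of √0.0127 = 0.11 of the block SD) removes 5% significance. The RT effect needs only about 0.0013. The criterion effect is sturdier and holds up to about 0.10.

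This rests on three assumptions: each contest is one fixed image set shared by its participants, sets differ between conditions, and blocks spread roughly evenly over contests. The actual ICC is unknown, so the documents do not show that any of these effects is absent. Neither systematic confounding nor a failure of the carry-over result follows. Repeated blocks from the same participant are a separate dependence and are not counted in these figures.

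**What to change.** 1. State in Methods how images were allocated to contests, whether everyone in a contest saw the same 80, and whether feedback and no-feedback contests shared images.
2. If sets are separate, refit the d', criterion and RT condition models with random effects for contest (or image) and participant, or analyse the 24 contest means with 20 error df. Take the condition tests and the Figure 2 and 3 intervals from that model, and report the estimated contest variance.
3. If feedback and no-feedback contests shared images, use image set as the random unit, crossed with feedback.
4. Keep the same-condition baseline in the carry-over analysis; a contest-specific baseline is not needed.

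The work is one added random term on data already collected. The documents do not list the fields of the posted file, so it must be confirmed that contest is recorded or can be rebuilt from condition and day. The price is wider intervals and less favourable condition p-values. Even at an ICC of zero, moving to 20 error df takes the d' p-value from 0.0002 to 0.003.
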